5.1 Statistical and Analytical Plan

5.1.1 Analyzable Populations

Both the efficacy and the safety analysis will be performed on the set of patients who received at least one injection of HUMIRA® (adalimumab).

In addition to the analysis of all patients who received HUMIRA® (adalimumab), certain subgroups may be defined and summarized, e.g. by age, sex, use of certain RA medications.

5.1.2 Planned Methods of Statistical Analysis

Demographics and Baseline Characteristics

Demographic and baseline variables will be described by summary statistics. For continuous data, n, mean, standard deviation, minimum, 1st quartile, median, 3rd quartile, and maximum will be presented. For categorical data, absolute and relative frequency will be calculated.

Safety Analyses

Adverse events will be analysed by presenting frequency and percentage. Furthermore, adverse events of special interest, e.g. serious adverse events, or adverse events leading to discontinuation of treatment with HUMIRA® (adalimumab), will be listed.

Efficacy Analysis

The efficacy analysis of continuous variables (e.g. joint count) will be done descriptively by presenting summary statistics and confidence intervals.

6 COMPLETION OF STUDY

The investigator will conduct this study in compliance with the protocol and all other applicable regulatory and legal requirements. Abbott SA/NV may terminate this study at any time, either in its entirety or at this site, for reasonable cause provided that written notice is submitted at a reasonable time in advance of the intended termination. The investigator may also terminate the study at their site for reasonable cause, after providing written notice to Abbott SA/NV a reasonable time in advance of the intended termination.

Appendix C

Guidance for Joint Evaluation after Preceding Therapeutic Joint Procedures

Procedure	Joints will not be assessed for:
Intraarticular steroid joint injection	3 months post injection
Joint synovectomy	3 months post surgery
Radiosynoviorthesis	3 months post synoviorthesis
Partial joint endoprostheses, without synovectomy	3 months post surgery
Partial joint endoprostheses and total synovectomy	no assessment
Total joint endoprostheses	no assessment
Joint resection	no assessment
Joint arthrodesis	no assessment

Appendix D

Health Assessment Questionnaire

In this section we are interested in learning how your illness affects your ability to function in daily life.

Please tick the response which best describes your usual abilities OVER THE PAST WEEK:

Without ANY Difficulty	With SOME Difficulty	With MUCH Difficulty	UNABLE To Do
------------------------------	-------------------------	----------------------------	-----------------

DRESSING & GROOMING

Are you able to:

- Dress yourself, including tying shoelaces and doing up buttons?
- Wash your hair?

RISING

Are you able to:

- Stand up from a straight chair?
- Get in and out of bed?

EATING

Are you able to:

- Cut up your meat?
- Lift a full cup or glass to your mouth?
- Open a new milk carton ?

WALKING

Are you able to:

- Walk outdoors on flat ground?
- Climb up five steps?

Please tick the response which best describes your usual abilities **OVER THE PAST WEEK:**

Without ANY Difficulty	With SOME Difficulty	With MUCH Difficulty	UNABLE To Do
------------------------------	----------------------------	----------------------------	-----------------

HYGIENE

Are you able to:

- Wash and dry your body?
- Have a bath?
- Get on and off the toilet?

REACH

Are you able to:

- Reach up for and take down a 5 lb object (e.g.: a bag of potatoes) from just above your head?
- Bend down to pick up clothing from the floor?

GRIP

Are you able to:

- Open car doors?
- Open jars which have been previously opened?
- Turn taps on and off?

ACTIVITIES

Are you able to:

- Go shopping?
- Get in and out of a car?
- Do chores such as vacuuming and gardening?

Appendix E Pregnancy Report Form

Investigator Name: _____ Subject Number: _____

Telephone Number: _____ Subject Initials: _____

Date of Birth: _____

Obstetric History

Gravida (present pregnancy not included) _____, Para _____, Aborta _____

Dosing Information

Dosing of HUMIRA® (adalimumab) Day 1 = _____

Birth Control Method

Has the patient used birth control measures? Yes _____ No _____
Unknown _____

Pregnancy

Date of 1st positive pregnancy test () serum _____ () urine _____

Date of last negative pregnancy test _____

Date of HUMIRA® (adalimumab) discontinuation _____

Dates of last menstrual period: Start: _____ End: _____

Estimated number of weeks gestation at 1st positive test _____

Is subject planning to carry pregnancy to term? _____ Yes _____ No _____

Estimated delivery date _____

Comments: _____

Investigator Signature: _____ **Date:** _____

Pregnancy Report Sheet (after delivery)

Date of delivery: _____

Route of delivery: _____

Birth weight/length: _____

Gender: _____

Apgar score: _____

Complications: _____

Outcome: _____

Any abnormalities (major or minor): _____

Labor and delivery report (attach)

1. METHODOLOGY

The purpose of this statistical analysis plan is to provide detailed information on the statistical analysis of the data of the ProAct study. The plan is based on the quotation dated 18 October 2017 and the mail dated 4 April 2017.

1.1 *Study Objective*

To evaluate the effectiveness and safety of adalimumab for the treatment of rheumatoid arthritis (RA), psoriatic arthritis (PsA) and ankylosing spondylitis (AS) in real life clinical practice.

1.2 *Available data*

The questionnaires table, as received on 5 February 2018, contained 47378 records, of which 5947 baseline visits. This database has been adapted by hardcoding in the programmation in order to resolve inconsistencies, double patients, misclassification of visits, add additional visit CRF pages, add additional AE pages. A total of 5920 patients of which 2836 rheumatoid arthritis patients, 1127 psoriatic arthritis patients (of which 197 Oligoarticular PsA) and 1957 ankylosing spondylitis patients were included in the analysis.

The parameter DAS28 was entered in the database from the moment the new Belgium reimbursement criteria for Humira were in place (2010).

Visits were scheduled at baseline, months 3, 6, 9 and 12, then every 6 months till 5 years.

1.3 *Patient Population*

All patients are to be considered in the analysis.

1.4 *Data Handling*

All data handling rules used during the analysis will be described in the section Methodology of the Statistical Report.

‘LT’ visits are visits added in the database for patients who were lost to follow-up in order to close the patient in the database. These visits will not be taken into account for any analysis.

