1 INTRODUCTION

HUMIRA®(adalimumab), a recombinant, full-length immunoglobulin is the first member of a new class of tumour necrosis factor (TNF) antibody compounds, developed to contain exclusively human sequences with a very high affinity for human TNF.

To date, more than 3,000 patients with rheumatoid arthritis (RA) have been treated subcutaneously with HUMIRA®(adalimumab) in controlled trials and more than 6,000 in phase IIIb studies and patient named basis programs in Europe, North America and Australia. HUMIRA®(adalimumab) was administered alone or in combination with methotrexate (MTX) or other disease-modifying anti-rheumatic drugs (DMARDs) or DMARD combinations.

HUMIRA®(adalimumab) has generally been well tolerated and has demonstrated therapeutic efficacy in the treatment of RA compared to placebo treatment. HUMIRA®(adalimumab) has also shown sustained efficacy in open-label long-term studies, however the data related to patients treated for four and five years is still limited (1, 2).

RA clinical development is largely completed although a number of long-term extension studies and studies for additional indications, e.g. Juvenile Rheumatoid Arthritis and early RA are ongoing.

HUMIRA®(adalimumab) was first approved by the Food and Drug Administration (FDA) for the treatment of patients with RA in the United States of America in December 2002, in Switzerland in April 2003, as well as in several Latin American countries. HUMIRA®(adalimumab) was approved in the European Union in September 2003. “HUMIRA®(adalimumab) is indicated for the treatment of moderate to severe, active rheumatoid arthritis in adult patients when the response to disease-modifying anti-rheumatic drugs including methotrexate has been inadequate. To ensure maximum efficacy, HUMIRA®(adalimumab) is given in combination with methotrexate. HUMIRA®(adalimumab) can be given as monotherapy in case of intolerance to methotrexate or when continued treatment with methotrexate is inappropriate”.

The data from the Psoriasis arthritis (PsA) controlled clinical trials support the conclusion that adalimumab has a favorable benefit/risk ratio in the treatment of subjects with PsA.

As from August 2005 EMEA has granted the approval for the use of Humira® (adalimumab) for the treatment of active and progressive psoriatic arthritis in adults when the response to previous disease-modifying anti-rheumatic drug therapy has been inadequate.

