2 STATISTICAL ANALYSIS

The analysis of the baseline data and prior anti-TNF treatment will be performed broken down by indication (RA, PsA, AS). Within each indication, baseline data will also be presented broken down by completed/not completed patients. Statistical tests will be performed to compare baseline data for patients completed/not completed the study.

The analysis of treatment duration and the evolution of different parameters over time, will be performed broken down by indication (RA, PsA, AS).

The analysis of adverse events will be performed for all patients together and broken down by indication (RA, PsA, AS):

- Overall
- Per year (up to 5 years)
- By cumulative yearly period (till 5 years)
- Incidence
- Incidence divided by total exposure to treatment (till 5 years).
- Reason for seriousness
- Serious adverse events: number of patients and incidence by system organ class and preferred term
- Non-serious adverse events: number of patients by system organ class and preferred term

If an adverse event has no onset date, the observation date will be taken as onset date. Events that are coded with multiple MedDRA Terms will be counted as separate event.

The percentages in the adverse event table are calculated as follows:

Table	Nominator	Denominator
Number of patients with an adverse event per year.	Number of patients treated in that year with at least one adverse event in that year.	Number of patients treated in that year.
Number of patients with an adverse event per cumulative year	Number of patients with at least one adverse event in that year or before.	Number of patients.
Number of adverse events by total exposure to treatment	Number of adverse events in that year or before.	The sum of the patients' treatment exposure time in that year or before.

The following tables will be presented:

Rheumatoid Arthritis

- 1 Baseline Characteristics– All Patients and Broken Down by Early Termination**
 - 1.1 Age
 - 1.2 Gender
 - 1.3 Disease Duration Before Inclusion
 - 1.4 Anti-TNF use Before Inclusion
 - 1.4.1 Anti-TNF Naïve / Experienced
 - 1.4.2 Types of Anti-TNF use Before Inclusion
 - 1.5 Physician's Assessment of Disease Activity
 - 1.6 Clinical Examination
 - 1.6.1 Joint Assessment (tender joints count, swollen joints count)
 - 1.6.2 Inflammatory Parameters (CRP, ESR)
 - 1.6.3 Physical Function (HAQ %)
 - 1.7 Concomitant Medication
 - 1.7.1 Concomitant Steroids
 - 1.7.2 Concomitant NSAIDs
 - 1.7.3 Concomitant Immunomodulators

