 - 1.7.4 Number of DMARDs Used
 - 1.7.5 Frequency of Use of Each Type of DMARD
 - 1.7.6 Combination of Types of DMARD Used
 - 1.8 Study Duration
 - 1.9 Results of the Tests

- 2 Follow-up Data**
 - 2.1 Treatment Duration
 - 2.1.1 Treatment Duration
 - 2.1.2 Treatment Duration Category
 - 2.1.3 Treatment Duration Broken Down by Year of Start Treatment
 - 2.1.4 Treatment Duration Broken Down by DAS28 Category at Window 2 (Month 6)
 - 2.2 Physician's Assessment of Disease Activity
 - 2.2.1 Physician's Assessment of Disease Activity in Each Window
 - 2.2.2 Physician's Assessment of Disease Activity - Difference from Baseline
 - 2.3 Clinical Examination
 - 2.3.1 Joint Assessment (tender joints count, swollen joints count) in Each Window
 - 2.3.2 Joint Assessment (tender joints count, swollen joints count) – Difference from Baseline
 - 2.3.3 Inflammatory Parameters (CRP, ESR) in Each Window
 - 2.3.4 Inflammatory Parameters (CRP, ESR) – Difference from Baseline
 - 2.3.5 Physical Function (HAQ %) in Each Window
 - 2.3.6 Physical Function (HAQ %) – Difference from Baseline
 - 2.3.7 Physical Function (HAQ %) - Number of Patients with >7.33% Reduction from Baseline
 - 2.3.8 DAS28 in Each Window
 - 2.3.9 DAS28 – Difference From Baseline
 - 2.3.10 DAS28 Category in Each Window

3 Adverse Events

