3.7.2 Number of Adverse Events by MedDRA System Organ Class and Preferred Term

Psoriatic Arthritis

1 Baseline Characteristics– All Patients and Broken Down by Early Termination

- 1.1 Age
- 1.2 Gender
- 1.3 Disease Duration Before Inclusion
- 1.4 Anti-TNF use Before Inclusion
 - 1.4.1 Anti-TNF Naïve / Experienced
 - 1.4.2 Types of Anti-TNF use Before Inclusion
- 1.5 Physician's Assessment of Disease Activity
- 1.6 Clinical Examination
 - 1.6.1 Joint Assessment (tender joints count, swollen joints count)
 - 1.6.2 Inflammatory Parameters (CRP, ESR)
 - 1.6.3 Physical Function (HAQ %)
 - 1.6.4 BSA with Psoriasis
 - 1.6.5 Patient's Numerical Rating Scale for Oligoarticular PsA Patients
 - 1.6.6 Physician's Numerical Rating Scale for Oligoarticular PsA Patients
- 1.7 Concomitant Medication
 - 1.7.1 Concomitant Steroids
 - 1.7.2 Concomitant NSAIDs
 - 1.7.3 Concomitant Immunomodulators
 - 1.7.4 Number of DMARDs Used
 - 1.7.5 Frequency of Use of Each Type of DMARD
 - 1.7.6 Combination of Types of DMARD Used
- 1.8 Study Duration
- 1.9 Results of the Tests

2 Follow-up Data

- 2.1 Treatment Duration
 - 2.1.1 Treatment Duration
 - 2.1.2 Treatment Duration Category
 - 2.1.3 Treatment Duration Broken Down by Year of Start Treatment
 - 2.1.4 Treatment Duration Broken Down by DAS28 Category at Window 2 (Month 6)
- 2.2 Physician's Assessment of Disease Activity
 - 2.2.1 Physician's Assessment of Disease Activity in Each Window
 - 2.2.2 Physician's Assessment of Disease Activity - Difference from Baseline
- 2.3 Clinical Examination
 - 2.3.1 Joint Assessment (tender joints count, swollen joints count) in Each Window
 - 2.3.2 Joint Assessment (tender joints count, swollen joints count) – Difference from Baseline
 - 2.3.3 Inflammatory Parameters (CRP, ESR) in Each Window
 - 2.3.4 Inflammatory Parameters (CRP, ESR) – Difference from Baseline
 - 2.3.5 Physical Function (HAQ %) in Each Window
 - 2.3.6 Physical Function (HAQ %) – Difference from Baseline
 - 2.3.7 Physical Function (HAQ %) - Number of Patients with >7.33% Reduction from Baseline
 - 2.3.8 DAS28 in Each Window
 - 2.3.9 DAS28 Category – Difference From Baseline
 - 2.3.10 DAS28 Category in Each Window
 - 2.3.11 BSA with Psoriasis in Each Window
 - 2.3.12 BSA with Psoriasis - Shift from Baseline
 - 2.3.13 Patient's Numerical Rating Scale for Oligoarticular PsA Patients in Each Window

- 2.3.14 Patient's Numerical Rating Scale for Oligoarticular PsA Patients - Difference from Baseline

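### DAS28 was entered only from 2010, so if entry followed visit date, the all-patient by-window tables 2.3.8 and 2.3.10 mix enrolment cohorts in proportions that change from window to window

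*SAP*

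**What the plan says.** SAP 1.2 gives DAS28 a calendar start: "The parameter DAS28 was entered in the database from the moment the new Belgium reimbursement criteria for Humira were in place (2010". It gives no month and does not say whether the rule applies to every visit from then on or only to patients enrolled from then on. It also does not say whether earlier values were added afterwards.

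SAP 1.5 assigns visits to windows, Month 3 to Month 60, by days since the patient's own baseline visit. SAP 1.3 puts all patients in the analysis.

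For RA, PsA and AS alike, SAP section 2 lists "2.3.8 DAS28 in Each Window" and "2.3.10 DAS28 Category in Each Window" with no restriction, stratum or denominator. Denominators are defined only for the adverse event tables. For RA there is also a paired table, "2.3.9 DAS28 – Difference From Baseline"; in PsA and AS its title is "2.3.9 DAS28 Category – Difference From Baseline".

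Neither document gives enrolment dates. Three points bear on them:
- Protocol section 1 says adalimumab "was approved in the European Union in September 2003". It treats the ankylosing spondylitis indication as expected from June 2006, so that amended text was written before then.
- Tables 2.3.9 (change from baseline) and 2.1.4 (grouping by Month 6 DAS28) presuppose some early-window values.
- The data are described "as received on 5 February 2018", and follow-up is five years.

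**The concern.** A calendar start for the measurement combined with windows in patient time makes eligibility for a DAS28 cell depend on when the patient enrolled. A patient enrolled in January 2007 could have no DAS28 before Month 36. A patient enrolled in 2011 could have one in every window.

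Protocol section 1 names maintenance of efficacy as a focus, and SAP 1.5 says the windows serve to show how parameters evolve. Tables 2.3.8 and 2.3.10 will therefore be read as a five-year course. If the two enrolment cohorts differ in DAS28 at the same window, the tables would show a movement that occurs in neither cohort.

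A difference is plausible. Inclusion requires prescribing within local reimbursement guidelines (Protocol 3.1.1), and DAS28 entry began when those criteria changed, so the cohorts may have been admitted under different rules. The documents do not say what changed, so this indicates neither size nor direction.

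**Working it through.** **The plan's own figures.** The SAP gives no DAS28 count and no enrolment dates to reproduce. The patient total agrees: 2,836 + 1,127 + 1,957 = 5,920.

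**Inputs.**
- DAS28 start D = 2010.0 (year from SAP 1.2; 1 January is assumed).
- Enrolment start s = 2004 to 2006 (assumed; EU approval September 2003, protocol amendment before June 2006).
- Enrolment end e = 2011 to 2013.1 (assumed; the upper value is February 2013, five years before data receipt).
- Uniform enrolment, equal retention in both cohorts, visits on the target month (all assumed).

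**Formula.** A patient can have a DAS28 at month m only if enrolled on or after D − m/12. With lo = max(s, D − m/12), the pre-2010 share of potential contributors is (D − lo)/(e − lo).

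| Window | e = 2011 | e = 2013.1 |
|---|---|---|
| Month 3 | 0.25/1.25 = 20% | 0.25/3.35 = 7.5% |
| Month 6 | 0.5/1.5 = 33% | 0.5/3.6 = 14% |
| Month 12 | 1/2 = 50% | 1/4.1 = 24% |
| Month 36 | 3/4 = 75% | 3/6.1 = 49% |
| Month 60, s = 2005 or earlier | 5/6 = 83% | 5/8.1 = 62% |
| Month 60, s = 2006 | 4/5 = 80% | 4/7.1 = 56% |

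A start anywhere from September 2003 to January 2005 gives the same Month 60 share, because patients enrolled before 2005 pass their Month 60 target before 2010.

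**By indication at Month 60.**
- PsA, start August 2005 (approval date in Protocol section 1) to 2006: from 4/7.1 = 56% to 4.4/5.4 = 81%.
- AS, start mid-2006: from 3.5/6.6 = 53% to 3.5/4.5 = 78%.

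**Sensitivity at Month 60.**
- Enrolment density rising linearly (t − s): s = 2006, e = 2013.1 gives 4²/7.1² = 32%; s = 2004, e = 2011 gives (6² − 1²)/(7² − 1²) = 73%.
- Enrolment density falling linearly (e − t): (7.1² − 3.1²)/7.1² = 81%; (6² − 1²)/6² = 97%.
- DAS28 entry from mid-2010 (uniform enrolment, share enrolled before that date): 4.5/7.1 = 63% to 5/5.5 = 91%.

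**Possible movement (illustration).** If the percentage with DAS28 below 2.6 is constant over time in each cohort but differs by 10 points between them, the apparent movement from Month 3 to Month 60 is 10 × (share at Month 60 − share at Month 3):
- smallest (s = 2006, e = 2013.1): 10 × (0.563 − 0.075) = 4.9 points;
- largest (s = 2005 or earlier, e = 2011): 10 × (0.833 − 0.200) = 6.3 points.

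The sign depends on which cohort is higher. With equal cohorts the movement is zero.

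**The case against.** The strongest counter-argument is that SAP 1.2 can be read another way. If DAS28 was entered only for patients enrolled from 2010, no cohort mix shifts between windows, and the fault is only an unlabelled subset. If earlier values were entered retrospectively, the point closes. This stands, so the finding is conditional and the SAP must say which case applies.

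The percentages rest on assumed dates and an assumed enrolment shape, and the 10-point difference is invented for illustration. This also stands. The figures show that the mix can shift substantially, not by how much it did.

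The weight is limited. DAS28 is not among the efficacy variables in Protocol 3.2.2 or 3.3.6. Joint counts, ESR, CRP, HAQ and the physician's assessment are all tabulated by window and as change from baseline. Protocol section 5 plans no inference, and SAP 1.2 itself discloses the 2010 rule. A footnote with n per window would meet part of the concern, but it would not separate the cohorts. A descriptive course still needs a comparable population or a label saying that it lacks one.

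Stronger readings that a reader might infer, and that the documents do not support:
- *The DAS28 course is biased.* The documents hold nothing on whether the cohorts differ, so bias may be zero and its direction is unknown.
- *A baseline-to-Month 60 contrast is distorted still more.* SAP 1.5 defines no baseline window and the section 1.6 baseline tables list no DAS28, so no specified cell shows that contrast.
- *The from-2010 patients give the true trend.* Permanent stoppers leave the study (Protocol section 3) and assessments are recorded only if made in routine practice (Protocol 3.2.2), so their composition changes too.
- *The HAQ and BASDAI tables share the fault.* The 2010 rule does not touch them.

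**Conclusion.** The point holds conditionally. If DAS28 was entered by visit date and not retrospectively, tables 2.3.8 and 2.3.10 in all three indications compare windows with different mixes of enrolment cohorts. The documents imply that enrolment spans 2010.

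Under the assumed uniform enrolment and equal retention, the pre-2010 share moves from about 7.5–20% at Month 3 to 56–83% at Month 60. Linear enrolment shapes widen the Month 60 range to 32–97%. A later end of enrolment lowers the shares. Beyond early 2013 this applies mainly to the earlier windows, because few patients enrolled after that could reach Month 60 before data receipt.

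This is a statement about composition. It becomes a distortion of the apparent course only as far as the cohorts differ. Values within one window remain a valid description of the patients assessed there. The paired table 2.3.9 and the by-window tables of other measures are not affected by this mix.

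**What to change.** 1. In SAP 1.2, state the date in 2010, whether DAS28 was entered by visit date or only for patients enrolled from then on, and whether earlier values were entered retrospectively.
2. If entry was by visit date, present 2.3.8 and 2.3.10 split by baseline visit before or from the DAS28 start date (or for patients with a baseline DAS28), beside the all-patient version, with n per window. Note that the from-2010 column removes the enrolment-era shift but still changes through discontinuation and unrecorded assessments.
3. If only patients enrolled from 2010 have DAS28, label the tables as that subset instead.

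The cost is SAP wording and extra columns. No new data are needed, because SAP 1.5 already uses the baseline visit date to compute the period. Year of treatment start is not a substitute, since patients enter with treatment ongoing (Protocol 3.1.1).

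The downside is smaller n per column. Under the assumed dates, (e − 2010)/(e − s) caps the from-2010 column, before attrition and unrecorded assessments, at:
- RA: 1/7 to 3.1/7.1, or 14–44% (405 to 1,238 of 2,836);
- PsA: 1/5.4 to 3.1/7.1, or 19–44% (209 to 492 of 1,127);
- AS: 1/4.5 to 3.1/6.6, or 22–47% (435 to 919 of 1,957).
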